## **5 SELECTION OF STUDY POPULATION**

### **5.1 Number of Subjects**

Approximately 50 subjects will be randomized. No more than 65 subjects will be randomized. There will be approximately 8 sites with each site randomizing 5 to 15 subjects.

### **5.2 Inclusion Criteria**

1. Subject and legal guardian understand the study procedures and agree to participate by giving assent and written informed consent, respectively. Legal guardian must be willing to authorize use and disclosure of protected health information collected for the study.
2. Subjects must be at least 12 years of age and no more than 16.9 years of age at the time of randomization.
3. Subjects must weigh at least 55 pounds at the Screening Visit.
4. Subjects must present with a clinical diagnosis of stable (at least 3 months) plaque-type psoriasis.
5. Subjects with psoriasis involving  $\geq$  10% BSA affected, not including the face, scalp, groin, axillae and other intertriginous areas.
6. Subjects must have an IGA grade of at least 3 (moderate) at the Baseline Visit.
7. All females must complete a urine pregnancy test (test must have a sensitivity of at least 25 mIU/mL for human chorionic gonadotropin) at the Baseline Visit (Visit 2), and the test result must be negative to be eligible for randomization.
8. Female subjects who are sexually active must agree to use contraception during the study. Reliable methods of contraception are:

- hormonal methods or intrauterine device in use  $\geq$  90 days prior to study product administration; or
- barrier methods plus spermicide in use at least 14 days prior to study product administration.
- partner has had a vasectomy at least 3 months previous to study product administration.

**Note:** Sexually inactive female subjects should be counseled to remain sexually inactive for the duration of the study and should be made to understand the possible risks involved in getting pregnant during the study. An abstinent female subject must agree that if she becomes sexually active during the study she will use an acceptable form of contraception.

9. Subjects must be in good general health as determined by the investigator and supported by the medical history and normal or not clinically significant abnormal vital signs (blood pressure and pulse).
10. Subjects whose results from the screening ACTH stimulation test are considered normal (blood cortisol level  $>18$  ug/dL at 30 minutes post stimulation) and show no other signs of abnormal HPA axis function or adrenal response.

### 5.3 Exclusion Criteria

1. Current diagnosis of unstable forms of psoriasis including guttate, erythrodermic, exfoliative or pustular psoriasis.
2. History of organ transplant requiring immunosuppression, HIV, or other immunocompromised state.
3. Have received treatment for any type of cancer within 5 years of the Baseline Visit.
4. Use within 60 days prior to the Baseline Visit of: 1) immunosuppressive drugs (e.g., tacrolimus, pimecrolimus), 2) systemic antipsoriatic treatment (e.g., methotrexate, cyclosporine, hydroxyurea), or 3) biologic treatment for psoriasis (e.g., infliximab, adalimumab, etanercept, ustekinumab, secukinumab, or alefacept).
5. Use within 30 days prior to the Baseline Visit of: 1) topical antipsoriatic drugs (salicylic acid, anthralin, coal tar, calcipotriene), 2) PUVA therapy, 3) systemic anti-inflammatory agents (e.g., mycophenolate mofetil, sulfasalazine, 6-thioguanine), or 4) UVB therapy.
6. Use within 30 days prior to the Screening Visit of any product containing corticosteroids. Inhaled, intraocular, intranasal, etc. steroids are not allowed.
7. Use within 14 days prior to the Baseline Visit of topical retinoids.
8. Subjects with known hypersensitivity to betamethasone dipropionate or any component of DFD-01.
9. Subjects who have an abnormal sleep schedule or work overnight.
10. Subjects who have participated in a study of an investigational product or device 60 days prior to the Baseline Visit.
11. Subjects unable to comply with study requirements.

12. Female subjects who are pregnant (or planning to become pregnant) or breast-feeding.
13. Subjects with a known history of acute adrenal crisis, Addison's disease or decreased adrenal output, low pituitary function or pituitary tumors.
14. Subjects who have a history of an adverse reaction to cosyntropin injection or similar test reagents.
15. Subjects with any history of illegal drug or alcohol use.

Subjects must not use the medications shown in [Table 1](#) for the period specified before the Baseline Visit (Visit 2).

**Table 1: Wash-out Table**

Product	Prior to ACTH stimulation test	Prior to Baseline Visit 2
Other investigational product or device		60 days
Immunosuppressive drugs (tacrolimus or pimecrolimus)		
Systemic antipsoriatic agents (methotrexate, cyclosporine, hydroxyurea)		
Biologic treatment for psoriasis (infliximab, adalimumab, etanercept, ustekinumab, secukinumab, or alefacept).		
Systemic anti-inflammatory agents (mycophenolate mofetil, sulfasalazine, 6-thioguanine)	30 days	
PUVA therapy		
UVB therapy		
Topical antipsoriatic drugs (salicylic acid, anthralin, coal tar, calcipotriene)		
Any product containing corticosteroids	30 days	
Topical retinoids		14 days

## **6 SUBJECT TREATMENT**

### **6.1 Investigational Products**

#### **6.1.1 Description**

The investigational product is:

- DFD-01 (betamethasone dipropionate) spray, 0.05%  
(120 mL spray bottle, Promius Pharma, LLC)

DFD-01 Spray will be provided by Promius Pharma, LLC, [name]. The spray formulation is a thin, white emulsion.

Initially, 6 bottles (DFD-01 Spray 0.05%) will be sent to each site. Additional bottles will be sent as needed. The spray product should be shaken before use.

#### **6.1.2 Labels and Packing**

Bottles will be packed one to a box. Labels on the bottles will be in English and Spanish and include product name, protocol number, a unique bottle number, investigational use warning, storage conditions, brief instructions for use, and sponsor name and address. Subjects will be asked to return bottles in the box.

#### **Bottle Label for DFD-01 Spray - Provided in English and Spanish Text**

DFD-01
Protocol: DFD01-CD-013      Bottle ID: FXXXX
Store at controlled room temperature 20°-25°C (68°-77°F); excursions permitted to 15°-30°C (59°-86°F). For Topical Use Only. Shake well before use. Apply twice daily as instructed.
Rub in gently and completely.
Caution: New Drug – Limited by Federal (or United States) Law to Investigational Use
Promius Pharma, LLC [name]

Labels on the box will be in English and Spanish and include product name, protocol number, a unique bottle number, investigational use warning, and storage conditions, brief instructions for use, and sponsor name and address. In addition, there will be a place to write the subject number and subject initials. The box-label will also have a tear-off panel that includes the protocol number and unique bottle number. The tear-off panel is to be affixed to the source document (drug dispensing record).

**Box Label for DFD-01 Spray - Provided in English and Spanish Text**

DFD-01 Protocol: DFD01-CD-013      Bottle ID: FXXXX Subject No.: _____      Subject Initials: _____
 
Store at controlled room temperature 20°-25°C (68°-77°F); excursions permitted to 15°-30°C (59°-86°F). For Topical Use Only. Shake well before use. Apply twice daily as instructed. Rub in gently and completely.
 
Caution: New Drug – Limited by Federal (or United States) Law to Investigational Use.
 
Promius Pharma, LLC, [name]
	
DFD-01 Protocol: DFD01-CD-013 Bottle ID: FXXXX Subject No.: _____ Subject Initials: _____
 
Tear off portion to be affixed to source document and filed with dispensing confirmation in Subject's chart.

---	---

### **6.1.3 Accountability**

Documentation of receipt, study product inventory, and return shipments of the study product must be maintained at each study site. Upon receipt of the study product supplies, an inventory must be performed. It is important that site personnel count and verify that the shipment contains all the items noted in the shipment record and that they are in good condition. At study completion, all containers of study product, used and unused, must be returned to the sponsor or designee.

In addition, a study product accountability log showing dispensing to and return by subjects must be maintained at each study site. Any dispensed bottles that are not returned to the clinic must be documented on the log.

### **6.1.4 Dispensing and Return**

One bottle of study product will be dispensed to subjects at the Baseline Visit (Visit 2) by study staff. The weight of the bottles should be recorded before dispensing. Additional bottles will be dispensed as needed. Partially filled bottles can be redispensed back to the subject. The study product to be dispensed for each subject will be identified by referring to the site randomization schedule. The tear-off panel is to be affixed to the source document. Subject initials and subject number must be written on the box label. Study staff will then dispense and instruct subject and legal guardian on study product use.

---

Dispensing and return of study product must be documented on the Investigational Product Site Dispensing and Return Log.

Subjects must return the used bottles even if empty throughout the trial. At the end of the trial, all used and unused bottles must be returned to the clinic for eventual destruction by the sponsor or designee. Any dispensed bottles that are not returned to the clinic must be documented on the log.

### **6.1.5 Storage**

Study products must be kept in a secure room temperature-controlled/monitored space at 20°-25°C (68°-77°F); excursions permitted to 15°-30°C (59°-86°F).

## **6.2 Treatment Regimen**

Subjects will use study product under the supervision and with help, if needed, of their legal guardian, twice daily with approximately 12 hours between applications for either 15 or 29 days starting on Day 1 during the study visit. Subjects will apply study product to all affected areas except the face, scalp, groin, axillae and other intertriginous areas. The target dose is at least 3 to 5 g per day (10 to 15 pumps of spray), twice daily, applied at approximately 2 mg/cm^2 on 10% BSA – 1500 cm^2). Subjects with greater than 10% BSA will apply more, as appropriate. All baseline affected areas and newly affected areas should be treated until the end of the study even if cleared. The investigator shall diagram the affected areas (in the source document), update the diagram at each visit, and remind the subjects and legal guardians where study product is to be applied at each visit using the diagram. Study product should be sprayed directly onto affected areas and rubbed in gently and completely. Study product should be applied after bathing, if applicable.

The first and last dates of treatment should be recorded in the CRF with the number of applications made on those days.

The first and last application of study product will be applied by the subjects or their legal guardian at the site under supervision. At the last visit, the bottle should be weighed before and after the application to determine the amount of study product applied for the last dose.

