## Methods:

This is a 15 or 29-day, randomized, multicenter, multi-dose, open label study. Subjects, who are at least 12 years old and not more than 16.9 years old with moderate to severe plaque psoriasis, will be randomized to treatment with either DFD-01 spray 15-day treatment or DFD-01 spray 29-day treatment in a 1:1 ratio. These investigational products will be applied twice daily to all affected areas on the body excluding face, scalp, groin, axillae and other intertriginous areas. Subjects must have  $\geq 10\%$  body surface area (BSA) treated to achieve maximal use exposure.

Subject visits will take place at Screening, Baseline (Day 1), Day 8, Day 15, Day 29 (as appropriate) and Day 43 or 57 (if needed to confirm recovery). Clinical determinations of disease severity will be conducted using the Investigator Global Assessment (IGA) for overall severity at each visit. Subjects will be tested for HPA axis function using the ACTH stimulation test (a cosyntropin i.v. or i.m. injection) at the Screening Visit (at least 14 days and no more than 28 days prior to Baseline) and at the End of Treatment Visit (i.e., Day 15 for the 15-day treatment arm or Day 29 for the 29-day treatment arm). If HPA axis is suppressed at the End of Treatment Visit, another test will be administered approximately 28 days later (at Day 43 or 57, as appropriate) to confirm recovery. The ACTH stimulation test will be repeated approximately every 28 days until recovery is confirmed (or until the cause of suppression is diagnosed). Pre-stimulation and post-stimulation cortisol levels will be measured in serum and saliva.

At the time of the screening ACTH stimulation test, a PK blood sample will be taken to obtain a baseline value (PK screening sample). At the End of Treatment Visit, subjects will apply the last dose of study product at the clinic up to 60 minutes after a pre-treatment PK blood sample is taken (0 hour – End of Treatment Visit). PK blood samples will then be collected at 1, 3 and 6 hours ( $\pm$  5 minutes) after application of the study product.

Local cutaneous safety evaluations (including atrophy, telangiectasia, pruritus, pain and burning/stinging) will be performed at Visits 2, 3, 4, and 5 (if appropriate). Other safety assessments include vital signs (blood pressure, pulse), urine pregnancy tests, and collection of adverse event data.

---

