**Investigational Product, Dose and Mode of Administration:**

---

DFD-01 (betamethasone dipropionate) Spray, 0.05%

The investigational product will be applied topically to all affected areas (i.e., those areas that were affected at Baseline, even if resolved, and new lesions that develop at any time during the treatment period) twice daily, approximately 12 hours apart. The target dose is at least 3 to 5 g per day (10 to 15 pumps, twice daily). Product is not to be applied to face, scalp, groin, axillae, or other intertriginous areas.

---

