**Study Schedule ( 29-day treatment arm)**

	Visit 1	Visit 2	Visit 3	Visit 4	Visit 5	Visit 6
	Screen a	Day 1 (Baseline)	Day 8 b	Day 15 b	Day 29 b (End of Treatment)	Day 57 c
Informed Consent	X					
Collect Demographic Data	X					
Inclusion and Exclusion Criteria	X	X				
Med History / Prior & Con Meds	X	X				
Vital Signs (BP, Pulse)	X	X	X	X	X	X
Urine Pregnancy Test	X d	X	X	X	X d	X d
Determine BSA	X	X			X	
IGA	X	X	X	X	X	
ACTH stimulation test g (blood and saliva samples)	X e				X h	X i
Local Cutaneous Safety Evaluation		X	X	X	X	
Randomization		X				
Weigh and Dispense Medication (as needed)		X	X	X		
Supervised treatment		X			X k	
Take Blood Samples for PK j	X				X	
Dispense/Review/Collect Study Diary		X	X	X	X	
Diagram affected areas to be treated		X	X	X		
Review Subject Instructions		X	X	X	X	
Collect and Weigh Used Containers			X	X	X	
Evaluate Compliance			X	X	X	
Review Concomitant Medications		X	X	X	X	X
Adverse Event Assessment		X f	X	X	X	X
End of Study					X	X

a No more than 60 days before Visit 2

b Allowed visit window  $\pm$  3 day

c If needed due to abnormal ACTH test result at End of Treatment Visit

d Pregnancy test just prior to ACTH stimulation test

e At least 14 days, and no more than 28 days, prior to Day 1

f Related to study procedures only

g ACTH stimulation test to be performed between 7:00 and 9:30AM

h ACTH stimulation test should be performed within 1 hour of time of when Screening test was performed

i ACTH stimulation test will be repeated until recovery (or is explained)

j Blood will be drawn at the time of the screening pre-stimulation ACTH test and at 0, 1, 3, 6 hours (+/-5 minutes) after application at End of Treatment Visit

k Weigh bottle before and after application

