## **6.3 Treatment and Protocol Compliance**

Subjects and legal guardians will be provided an instruction sheet specific for the study product, along with a diagram of affected areas to be treated. Study staff should review the instruction sheet and diagram with the subjects and their legal guardian to ensure protocol compliance. If new affected areas appear between visits, the subject may start treating the new area between visits. Treatment areas are to be updated on the diagram at each visit.

At each visit, the investigator or designee will interview subjects and their legal guardian concerning treatment compliance and ask if any doses have been missed. The investigator will also ask about compliance with protocol requirements. Protocol deviations will be recorded in the subject's chart and Protocol Deviation Form. A Protocol Deviation Form is not needed for

---

missed visits, missed applications, out-of-window visits and missing data. These items will be apparent from the missing data on the CRF and will be identified programmatically during data analysis for purposes of reporting. The sponsor should be consulted before discontinuing subjects due to protocol deviations unless safety is a concern.

Subjects/legal guardian will be provided a diary card for documenting the dates of applications. The subjects and legal guardian will review the diary card with the investigator or designee at each visit. The number of applications and the number of missed applications will be recorded on the CRF. By definition, there are no missed applications after the last date of treatment even if recorded on the diary.

In addition, bottles of study product will be weighed before dispensing and before and after the last application. These weights should be entered into the CRF.

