### **7.9.2 Visit 2 - Day 1 - Baseline Visit**

1. Update the medical history and concomitant medications. Any medical event (not related to a protocol intervention) that occurred since informed consent was signed should be recorded as medical history if still ongoing.
2. Collect adverse events. Any new medical event, need for new medication, or change in medication dosing caused by a protocol procedure performed at the Screening Visit should

be considered an adverse event except for worsening of psoriasis.

3. Confirm eligibility according to inclusion/exclusion criteria.
4. Conduct urine pregnancy test on female subjects. Record method of contraception, as applicable, on source only.
5. Collect vital signs (blood pressure, pulse).
6. Conduct clinical assessments:
  - a. IGA ([Table 2](#))
  - b. Local cutaneous safety evaluation for clinically significant atrophy and telangiectasia in areas to be treated. The investigator should also ask the subject if any burning/stinging, pain, or itching has occurred in the areas to be treated in the last 14 days.
  - c. Diagram affected areas to be treated (excluding face, scalp, axillae, groin and other intertriginous areas).
  - d. Determine BSA excluding face, scalp, axillae, groin and other intertriginous areas.
7. Randomize the subject by referring to the randomization schedule and dispense study product to the subject/legal guardian. The tear-off panel from the box is to be affixed to the source document. Make a note on source document regarding treatment duration.
8. Instruct subject and legal guardian on study product use. Review the appropriate Subject Instructions with subject (See [Appendix 2](#)). Using the diagram of affected areas, have the subject treat the affected areas under supervision after weighing the study product.
9. Dispense and review use of diary. Remind subject and legal guardian to record actual application dates and/or potential adverse events as well as any medication used in the diary and to bring diary to each visit.
10. Schedule next visit.
11. Complete CRF for all subjects including screen failures. Only enter concurrent medical conditions and concomitant medications on the CRF.

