**APPENDIX 2**  
**Subject Instructions - Spray**

1. You have been given a bottle of study medication. **Shake well before using.** Spray study medication directly onto each of your psoriasis lesions as instructed by the study nurse. Refer to the diagram provided. Apply study medication to all areas shown on the body diagram even if clear. Also apply study medication to new areas that may appear between visits. Apply study medication in the morning and at bedtime, approximately 12 hours apart. You will need to use at least 15-20 sprays of study medication each time. You can use more if needed. Massage lightly after application until medication disappears. If bathing at the treatment time, apply medication after bathing.
2. The study medication is for external use only. The study medication should not be used on the scalp, face, underarms, or groin area. Also avoid contact with eyes and lips. The application areas must not be bandaged, covered, or wrapped.
3. Always wash hands before applying the study medication and thoroughly after applying.
4. Store medication at room temperature.
5. If you have any questions, please ask the study coordinator or nurse.
6. The study medication may cause some irritation or discomfort. Tell your doctor about any reactions. If the reaction becomes severe, stop using the study medication and call the doctor.
7. Write down the date and time (am or pm) when you apply the study medication in your study diary.
8. Do not let anyone else use the study medication. Keep the medication out of the reach of children and pets. Use of the study product should be done under the supervision of the legal guardian.
9. Return all containers in the box at every study visit.
10. Bring your study diary to every visit.
11. If you cannot make a scheduled visit, please contact the study office as soon as possible to re-schedule another date.
- 12. Do not use study medication on the morning of your last study visit.**
13. If you have to discontinue participation in the study for any reason, notify the study office immediately. A visit will be scheduled for a final examination of psoriasis and to collect the containers and your diary. This visit is important for your safety.

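### The protocol body and its subject instruction sheet give different minimum spray counts (10 to 15 versus at least 15 to 20 per application), and Section 6.2 does not say whether its 2 mg/cm² rate is per day or per application

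*Combined protocol and SAP*

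**What the plan says.** Three places in the protocol state how much product to apply.

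- Synopsis, Investigational Product, Dose and Mode of Administration: "The target dose is at least 3 to 5 g per day (10 to 15 pumps, twice daily".
- Section 6.2: "The target dose is at least 3 to 5 g per day (10 to 15 pumps of spray), twice daily, applied at approximately" 2 mg/cm² on 10% BSA, which it equates to 1500 cm². Subjects with a larger affected area are to apply more. Here the twice-daily wording stands outside the first bracket, and the sentence ends with a closing bracket that has no opening partner.
- Appendix 2, Subject Instructions, item 1: "You will need to use at least 15-20 sprays of study medication each time", in the morning and at bedtime, with more allowed if needed.

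The Appendix 2 sheet is in active use. Section 6.3 provides that "Study staff should review the instruction sheet and diagram with the subjects and their legal guardian to ensure protocol compliance". Section 7.9.2, step 8, instructs staff at Visit 2: "Review the appropriate Subject Instructions with subject", in the same step as the first supervised application. Both study schedules carry a row "Review Subject Instructions", marked at Visits 2 to 5 in the 29-day arm and Visits 2 to 4 in the 15-day arm.

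No section explains the difference in counts, and none gives a weight per pump.

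**The concern.** The body and the appendix are meant to describe one regimen, yet they set different minimum spray counts. Section 6.3 treats the sheet as a tool for protocol compliance, so staff who go through it with an adolescent and guardian are conveying a floor that differs from the one in Section 6.2.

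Both study objectives are framed under maximal use conditions, and the primary safety variable is an abnormal cortisol response. The amount applied is therefore the exposure under study, and its instruction should read the same wherever it appears. The diary records when applications are made, and the CRF records how many were made and missed. Neither is said to record sprays per application, so the records would not show which count a subject worked to.

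The rate in Section 6.2 adds a smaller difficulty. A reader who wants to check the gram target against the rate must first guess whether the rate is per day or per application, and the two guesses differ by a factor of two.

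**Working it through.** **Spray count**

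Inputs: 10 to 15 pumps per application (Synopsis; same count in Section 6.2); at least 15 to 20 sprays per application (Appendix 2, item 1); two applications a day (all three places). One pump is taken to be one spray. No pump weight is needed.

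| | Protocol body | Appendix 2 sheet | Ratio |
|---|---|---|---|
| Low end, per application | 10 | 15 | 15/10 = 1.5 |
| High end, per application | 15 | 20 | 20/15 = 1.33 |
| Low end, per day | 2 × 10 = 20 | 2 × 15 = 30 | 1.5 |
| High end, per day | 2 × 15 = 30 | 2 × 20 = 40 | 1.33 |

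The ranges share one value: 15 per application, or 30 per day. Taking cases:

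- 10 to 14 sprays: within the body's count, below the sheet's floor.
- 15 sprays: meets both.
- More than 15 sprays: follows the sheet and also meets the body's count, because the body's target is a minimum.

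**Application rate**

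Inputs: about 2 mg/cm² and 1500 cm² for 10% BSA (Section 6.2).

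Rate × area = 2 mg/cm² × 1500 cm² = 3000 mg = 3 g.

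- If the rate is a daily total: 3 g/day. This reproduces the lower end of the stated 3 to 5 g/day.
- If the rate is per application: 2 × 3 g = 6 g/day. This lies above the stated range, though it does not breach a target worded as a minimum.

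The daily reading fits the stated figure better. The wording, with twice daily placed immediately before the rate, permits the other.

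**The case against.** The strongest reply is that both counts are floors. Neither text sets a ceiling, Section 6.2 tells subjects with larger areas to use more, and the sheet allows more. Anyone who follows the sheet meets the body's count as well, so the 1.33 ratio at the high end compares numbers that are not limits. Falling between the two floors requires a subject to depart from the sheet, or staff to coach to the lower count. Nothing in the protocol makes a spray count a deviation criterion. This stands, and it limits the practical consequence. It does not explain why one protocol gives two different minimums.

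The plan also protects its results. Section 11.5.1 summarises total use from bottle weights and gives the last dose by weight. Maximal use has its own area criterion in the Synopsis Methods (10% or more "body surface area (BSA) treated to achieve maximal use exposure"). The summaries are descriptive, and none uses the target amount. This stands too: no bias in a planned analysis follows.

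Four stronger readings are tempting and are not supported.

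- *Staff work to a number foreign to the protocol.* Appendix 2 is part of the protocol, is listed in its contents and is cited at Visit 2. The conflict is between body and appendix.
- *The 5 g end cannot come from 2 mg/cm².* Read as a daily total, 5000 mg ÷ 2 mg/cm² = 2500 cm², and 2500/1500 × 10% = 16.7% BSA. That agrees with Section 6.2, where subjects above 10% BSA apply more. The text does not require the whole range to come from 1500 cm².
- *The target covers less than the entry area.* Read per application, 3 to 5 g/day would cover 5% to 8.3% BSA at 2 mg/cm², below the entry minimum of "10% BSA affected, not including the face, scalp, groin, axillae and other intertriginous areas". That relies on the reading that fits the gram range less well and treats a minimum as a cap.
- *Exposure differs 1.5-fold.* The 1.5 is a ratio of counts. With no pump weight in the documents, it cannot be turned into grams without assuming how the gram and pump ranges correspond.

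**Conclusion.** The inconsistency is real and can be seen from the text alone. The body asks for 10 to 15 sprays per application and the sheet for at least 15 to 20; the floors differ 1.5-fold and the ranges touch only at 15. This rests on two assumptions: a pump and a spray are the same thing, and the count in Section 6.2 is per application. The Synopsis supports the second by placing the twice-daily wording inside its bracket. A reader might infer from the punctuation of Section 6.2 alone that 10 to 15 is a daily total, which would widen the gap, but the Synopsis does not support that.

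The rate is a lesser matter: an ambiguous phrase with an unmatched bracket, worth 3 g/day or 6 g/day according to the reading, with the daily reading agreeing with the stated lower end.

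The consequence is for the consistency of a dosing instruction given to adolescents and guardians under maximal use conditions. The documents do not support a claim that any planned summary is invalid or that subjects who follow the sheet would be under-treated relative to the body.

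**What to change.** The sponsor must reconcile the Synopsis dose paragraph, Section 6.2 and Appendix 2, item 1, so that all three give the same:

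- spray count per application;
- amount per application and per day;
- basis for the 2 mg/cm² rate (per application or per day), with the bracket in Section 6.2 repaired.

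Stating the weight per pump would let a reader check grams against sprays. Whichever text proves inconsistent should be corrected; this review does not say which figure is right.

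The cost is a wording amendment to the protocol. If the sheet is the text that changes, a corrected sheet must be reissued with IRB handling. No new data collection and no change to the planned summaries is needed.
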